7.2.4. Other Efficacy Analyses

7.2.4.1. Pharmacokinetic and Pharmacodynamic Analyses

All pharmacokinetic analyses will be conducted on the PK Analysis Set. PD analyses will be conducted on the FA Set.

Mean serum ALXN1210 concentrations versus nominal time, and individual serum ALXN1210 concentrations versus actual time will be graphically presented.

Individual serum concentration data for ALXN1210-treated patients, with actual sampling dates and times, will be used to derive the PK parameters by noncompartmental analyses, using Phoenix WinNonlin 6.3 or more current version.

The following PK parameters will be estimated following the first (loading) and last (maintenance) dose in each cohort: C_{max} , C_{max} dose normalized, t_{max} , AUC_t (first dose only), and AUC_t dose normalized (first dose only), $AUC_{0-\tau}$ (last maintenance dose only) and $AUC_{0-\tau}$ dose normalized (last maintenance dose only), and C_{trough} . Descriptive statistics (mean, SD, CV, median, minimum, maximum, geometric mean, and geometric %CV) of the serum concentration and PK parameter summaries will be provided, as appropriate.

The summaries of PK parameter results will be reported to 2 decimal places except for CV and geometric CV which will be reported to 1 decimal place.

Assessment of steady state and accumulation at steady state also will be evaluated. Additional PK analyses, such as assessment of PK linearity, may be conducted.

The PD effects of ALXN1210 administered IV will be evaluated by assessing changes and percent changes in serum total and free C5 concentrations, and cRBC hemolysis over time. Assessments of PK-PD relationships may be explored using data from this study or in combination of data from other studies.

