### 3. LIST OF ABBREVIATIONS AND DEFINITIONS OF TERMS

**Table 2: Abbreviations and Special Terms**

| Abbreviation or Term | Explanation  |
|----------------------|--|
| $\lambda_z$          | apparent terminal-phase elimination rate constant  |
| %CV                  | percent coefficient of variance  |
| ADA                  | antidrug antibody/ies  |
| ADCC                 | antibody-dependent cell-mediated cytotoxicity  |
| AE                   | adverse event  |
| Alexion              | Alexion Pharmaceuticals, Inc.  |
| AUC t     | area under the serum concentration-versus-time curve from time 0 (dosing) to the last quantifiable concentration     |
| AUC τ     | area under the concentration-versus-time curve from time 0 (dosing) to the end of the dosing interval                |
| AUC 0-x   | area under the concentration-versus-time curve from time 0 (dosing) to X days postdosing                             |
| AUC ∞     | area under the concentration-versus-time curve from time 0 (dosing) extrapolated to infinity                         |
| BMI                  | body mass index  |
| BNP                  | brain natriuretic peptide  |
| BP                   | blood pressure   |
| C5                   | complement component 5   |
| CDC                  | complement-dependent cytotoxicity  |
| CL                   | total clearance  |
| C max     | maximum observed serum concentration   |
| C min     | minimum observed serum concentration   |
| C trough  | the serum concentration at the end of the dosage interval τ  |
| cRBC                 | chicken red blood cell   |
| CTCAE                | Common Terminology Criteria for Adverse Events   |
| CV                   | coefficient of variance  |
| DMC                  | Data Monitoring Committee  |
| ECG                  | electrocardiogram  |
| eCRF                 | electronic case report form  |
| eGFR                 | estimated glomerular filtration rate   |
| EOI                  | end of infusion  |
| EORTC                | European Organisation for Research and Treatment of Cancer, Quality of Life Questionnaire-Core 30 Scale, version 3.0 |
| FACIT-Fatigue        | Functional Assessment of Chronic Illness Therapy-Fatigue Scale, version 4  |
| FAS                  | Full Analysis Set  |
| GCP                  | Good Clinical Practice   |
| HIV                  | human immunodeficiency virus   |

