**Table 3: Dosing Schedule**

| Cohort | Patients | Induction                             | Maintenance  |
|--------|----------|---------------------------------------|--|
| 1      | 6        | 1400 mg on Day 1
1000 mg on Day 15 | 
 
1000 mg on Day 29 and then every 28 days or 4 weeks (Days 57, 85, 113, 141, 169, 197, 225, 253, 281, 309, 337, 365, 393, 421, 449, 477)
 
Weight-baseda dose on Day 533 and then every 8 weeks (Days 589, 645, 701, 757, 813, 869, 925, 981, 1037b, 1093, 1149, 1205, 1261, 1317, 1373, 1429, 1485, 1541, 1597, 1653, 1709, 1765, 1821, 1877, 1933, 1989, 2045, 2101)
 
 |
| 2      | 6        | 2000 mg on Day 1
1600 mg on Day 22 | 
 
1600 mg on Day 43 and then every 42 days or 6 weeks (Days 85, 127, 169, 211, 253, 295, 337, 379, 421)
 
Weight-baseda dose on Day 463 and then every 8 weeks (Days 519, 575, 631, 687, 743, 799, 855, 911, 967, 1023b, 1079, 1135, 1191, 1247, 1303, 1359, 1415, 1471, 1527, 1583, 1639, 1695, 1751, 1807, 1863, 1919, 1975, 2031, 2087)
 
                              |
| 3      | 6        | 1600 mg on Day 1
1600 mg on Day 15 | 
 
2400 mg on Day 29 and then every 56 days or 8 weeks (Days 85, 141, 197, 253, 309, 365, 421)
 
Weight-baseda dose on Day 477 and then every 8 weeks (Days 533, 589, 645, 701, 757, 813, 869, 925, 981b, 1037, 1093, 1149, 1205, 1261, 1317, 1373, 1429, 1485, 1541, 1597, 1653, 1709, 1765, 1821, 1877, 1933, 1989, 2045, 2101)
 
  |
| 4      | 6 to 8   | 3000 mg on Day 1                      | 
 
5400 mg on Day 29 and then every 84 days or 12 weeks (Days 113, 197, 281, 365, 449, 533, 617, 701, 785, 869, 953b, 1037, 1121, 1205, 1289, 1373, 1457, 1541, 1625, 1709, 1793, 1877, 1961, 2045)
 
  |

a 3000 mg for patients weighing  $\geq 40$  to  $< 60$  kg, 3300 mg for patients weighing  $\geq 60$  to  $< 100$  kg, and 3600 mg for patients weighing  $\geq 100$  kg.

- b Beginning on Day 953 for patients in Cohort 4, Day 981 for patients in Cohort 3, Day 1023 for patients in Cohort 2, and Day 1037 for patients in Cohort 1, patients will switch from the 10 mg/mL ALXN1210 unit dose formulation to the 100 mg/mL ALXN1210 unit dose formulation, while remaining on their current dose regimen.

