## 16.7. Pharmacokinetic Analysis

Individual serum concentration data for ALXN1210-treated patients, with actual sampling dates and times, will be used to derive the PK parameters by noncompartmental analyses, using Phoenix® WinNonlin® (Pharsight Corporation, St Louis, Missouri) Version 6.3 or higher. The PK samples collected on or after Day 1149 for Cohort 1, Day 1135 for Cohort 2, Day 1093 for Cohort 3, or Day 1121 for Cohort 4 will be stored and may be assayed if considered necessary for the purpose of medical monitoring.

The following PK parameters will be estimated: maximum observed serum concentration ( $C_{max}$ ) after each dose, time to maximum observed serum concentration ( $t_{max}$ ), minimum observed serum concentration ( $C_{min}$ ), the observed serum concentration at the end of the dosage interval  $\tau$  ( $C_{trough}$ ), area under the serum concentration-versus-time curve from time 0 (dosing) to the last quantifiable concentration ( $AUC_t$ ), area under the concentration-versus-time curve from time 0 (dosing) to the end of the dosing interval ( $AUC_\tau$ ), apparent terminal-phase elimination rate constant ( $\lambda_z$ ), terminal elimination half-life ( $t_{1/2}$ ), and, if possible, total clearance (CL) and volume of distribution at steady state ( $V_{ss}$ ). Attainment of steady state and accumulation at steady state also will be determined. Dose proportionality and time linearity in PK parameters may be assessed.

Mean serum ALXN1210 concentrations versus nominal time and individual serum ALXN1210 concentrations versus actual time will be graphically presented. Descriptive statistics (mean, SD, CV, median, minimum, maximum, geometric mean, and geometric %CV) of the serum concentration and PK parameter summaries will be provided, as appropriate.

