3. LIST OF ABBREVIATIONS AND DEFINITIONS OF TERMS

The following abbreviations and acronyms are used in this SAP.

Table 1: Abbreviations and acronyms

Abbreviation or acronym	Explanation
ADA	antidrug antibody
AE	Adverse event
ALT	Alanine aminotransferase (SGPT)
ANCOVA	Analysis of Covariance
ATC	Anatomical Therapeutic Chemical
AST	Aspartate aminotransferase (SGOT)
AUC _t	area under the serum concentration-versus-time-curve from time 0 (dosing) to the last quantifiable concentration
AUC _{0-τ}	area under the concentration-versus-time-curve from time 0 (dosing) to the end of the dosing interval
BMI	Body mass index
cm	centimeters
BNP	brain natriuretic peptide
BP	Blood pressure
CKD	Chronic kidney disease
CI	Confidence Interval
CL	Total clearance
C _{max}	maximum observed serum concentration
C _{min}	minimum observed serum concentration
eRBC	chicken red blood cell
CS	Clinically significant
CSR	Clinical Study Report
CTCAE	Common Terminology Criteria for Adverse Events
CV	Coefficient of variance
DMC	Data Monitoring Committee
ECG	Electrocardiogram
eCRF	Electronic Case Report Form
eGFR	Estimated Glomerular Filtration Rate
EOI	End of infusion
EORTC QLQ-C30	European Organisation for Research and Treatment of Cancer, Quality of Life Questionnaire-Core 30 Scale
FA	Full Analysis
FACIT-FATIGUE	Functional Assessment of Chronic Illness Therapy-Fatigue
FDA	Food and Drug Administration
GEE	Generalized estimating equations
GOF	Goodness-of-fit
HR	Heart rate
IV	intravenous(ly)
LDH	lactate dehydrogenase
LOCF	Last Observation Carried Forward
MAVE	major adverse vascular event
MedDRA	Medical Dictionary for Regulatory Activities
MMRM	mixed model for repeated measures
PD	Pharmacodynamic
PK	Pharmacokinetic

Abbreviation or acronym	Explanation
PNH	paroxysmal nocturnal hemoglobinuria
pRBC	Peripheral red blood cell
PT	Preferred Term (MedDRA)
PTAEs	Pre-Treatment Adverse Events
QoL	quality of life
QTcF	QT interval corrected using Fridericia's formula
RBC	Red blood cell
RR	Respiration rate
SAE	Serious adverse event
SAS [®]	Statistical Analysis Software [®]
SAP	Statistical Analysis Plan
SD	Standard deviation
SOC	System Organ Class (MedDRA)
TEAEs	Treatment-Emergent Adverse Events
t _{max}	time to maximum observed serum concentration
ULN	upper limit of normal
VAS	Visual analog scale
V _{ss}	volume of distribution at steady state
WHO-DRUG	World Health Organization Drug Dictionary

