4. DESCRIPTION OF THE PROTOCOL

ALXN1210-PNH-201 is a Phase 2, open-label, multiple ascending dose study to evaluate the efficacy, safety, tolerability, immunogenicity, PK, and PD of multiple doses of ALXN1210 administered IV to patients with PNH who have not been previously treated with a C5 complement inhibitor.

Four treatment cohorts and up to 26 patients (at least 6 per cohort) are planned for enrollment, with at least 20 patients planned for evaluation. All patients are to be screened for study eligibility after providing written informed consent to participate. Patients who fail to meet any of the eligibility criteria may be rescreened once for study participation, at the discretion of the Investigator.

Patients enrolled in Cohort 1 will receive induction doses of ALXN1210 of 1400 mg on Day 1 and 1000 mg on Day 15. On Day 29, they will receive the first of 8 maintenance doses of 1000 mg of ALXN1210 (administered every 28 days or 4 weeks) (Table 1). Patients enrolled in Cohort 2 will receive induction doses of ALXN1210 of 2000 mg on Day 1 and 1600 mg on Day 22. On Day 43, they will receive the first of 5 maintenance doses of 1600 mg of ALXN1210 (administered every 42 days or 6 weeks). Patients enrolled in Cohort 3 will receive induction doses of ALXN1210 of 1600 mg on Day 1 and 1600 mg on Day 15. On Day 29, they will receive the first of 4 maintenance doses of 2400 mg of ALXN1210 (administered every 56 days or 8 weeks). Patients enrolled in Cohort 4 will receive an induction dose of ALXN1210 of 3000 mg on Day 1. On Day 29 they will receive the first of 3 maintenance doses of 5400 mg of ALXN1210 (administered every 84 days or 12 weeks). The first 2 patients in Cohort 4 will receive their induction dose (3000 mg) at least 1 day apart. The third patient will receive the induction dose at least 7 days after the second patient has received the induction dose.

If additional patients are screened and are eligible for enrollment before a dose-escalation decision has been made by the DMC for any cohort, those patients will be assigned to the active cohort with the lowest dose level.

[figure not shown]
On Day 253, patients will continue treatment in a long-term Extension Period of the study, at the same maintenance dose and frequency as their final dose of ALXN1210 administered during the Treatment Period.

The dosing schedule is provided in Table 1 and the overall study design is presented in Figure 1 .

Table 1: Dosing Schedule

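### First-dose AUCt covers 14, 21, 14 and 28 days in Cohorts 1-4, so its dose-normalised value cannot be compared across all cohorts as planned

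*SAP*

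**What the plan says.** SAP 7.2.4.1 plans, after the first dose in each cohort, "AUC_t (first dose only), and AUC_t dose normalized (first dose only", with descriptive statistics. SAP Section 3 defines AUCt as the "area under the serum concentration-versus-time-curve from time 0 (dosing) to the last quantifiable concentration". No common time window is set. The same sentence of 7.2.4.1 also plans dose-normalised Cmax after the first and last dose, and dose-normalised AUC0-tau after the last maintenance dose.

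SAP Section 4 gives the schedule:

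- Cohort 1: "induction doses of ALXN1210 of 1400 mg on Day 1 and 1000 mg on Day 15".
- Cohort 2: "induction doses of ALXN1210 of 2000 mg on Day 1 and 1600 mg on Day 22". Protocol Table 3 agrees.
- Cohort 3: "induction doses of ALXN1210 of 1600 mg on Day 1 and 1600 mg on Day 15".
- Cohort 4: 3000 mg on Day 1, with the next dose (5400 mg) on Day 29.

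Protocol 16.7 also lists AUCt and adds: "Dose proportionality and time linearity in PK parameters may be assessed". SAP 7.2.4.1 likewise leaves a linearity assessment optional. Neither section names the parameter it would use. Protocol Table 2 defines AUC0-x as the "area under the concentration-versus-time curve from time 0 (dosing) to X days postdosing", but neither Protocol 16.7 nor SAP 7.2.4.1 uses it.

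**The concern.** The usual reason to divide an AUC by dose is to compare exposure per mg between doses. That works only if the areas cover the same time span, or if each captures nearly all of the total exposure. Neither holds here. The drug is still present when Dose 2 is given, so each first-dose area is cut off at a point set by the cohort's schedule.

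The cut-off also tends to fall later as the first dose rises: 14 days at 1400 and 1600 mg, 21 days at 2000 mg and 28 days at 3000 mg. Constant clearance would therefore give a row in which exposure per mg rises with dose. What is at stake is the reading of that row, and any first-dose linearity statement based on it.

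**Working it through.** The documents give no figure for this point, so there is nothing to reproduce.

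**Windows.** Protocol Table 17 places the last sample belonging to Dose 1 at the predose sample of Dose 2. The Day 22 sample in Cohorts 1 and 3 and the Day 29 sample in Cohort 2 come a week after Dose 2. The windows are:

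- Cohorts 1 and 3: 15 − 1 = 14 days
- Cohort 2: 22 − 1 = 21 days
- Cohort 4: 29 − 1 = 28 days

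**Half-life.** Protocol 6.2 gives about 43 days (39-48) from population PK, and about 31 days (27-38) from single doses in healthy volunteers. Both central estimates exceed every window.

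**Formula.** For a linear one-compartment IV model, AUC(0-T)/Dose = (1/CL) × (1 − 2^(−T/t½)). The bracket is the share of AUC(0-infinity) captured, and the ratio of two brackets is the artefact.

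| Half-life | 14 d | 21 d | 28 d | Cohort 2 vs 1 and 3 | Cohort 4 vs 1 and 3 | Cohort 4 vs 2 |
|---|---|---|---|---|---|---|
| 31 d | 0.269 | 0.375 | 0.465 | 1.39 | 1.73 | 1.24 |
| 43 d | 0.202 | 0.287 | 0.363 | 1.42 | 1.80 | 1.26 |
| 48 d | 0.183 | 0.262 | 0.333 | 1.43 | 1.82 | 1.27 |

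Ratios are taken before rounding. Cohort 3 against Cohort 1 is 1.00 in every row. At 27 days, the lowest half-life in the documents, Cohorts 2 and 4 give 1.38 and 1.70.

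**Undivided AUCt at 43 days, Cohort 4 against Cohort 1.** (3000 × 0.363)/(1400 × 0.202) = 1089/282.8 = 3.85, for a dose ratio of 3000/1400 = 2.14.

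**Distribution phase (assumed; the documents give no figures).** Suppose 30-50% of the initial concentration is lost with a half-life of 1-4 days, and the terminal half-life is 31 or 43 days. The exact areas then give 1.30-1.40 for Cohort 2 and 1.54-1.76 for Cohort 4. Log-linear trapezoids on the planned samples give 1.36-1.43 and 1.50-1.67. The artefact shrinks, mostly in Cohort 4, but remains.

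**Other rows in the same table.** Dose-normalised Cmax does not depend on the window. I summed all scheduled doses under the one-compartment model at 31 and 43 days. AUC0-tau per mg after the last maintenance dose is then 0.999 to 1.011 times 1/CL in the four cohorts, so that row is flat.

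**Common 14-day window.** Under one-compartment decline every ratio becomes 1.00. Cohorts 1, 3 and 4 all have end-of-infusion, 4-hour and Day 15 samples. Cohort 2 has none between 4 hours and Day 22. Log-linear interpolation to Day 15 under the same assumed distribution phases leaves Cohort 2 at 1.04-1.10 relative to Cohort 1.

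**The case against.** The strongest reply is that this is one descriptive row, with about six patients per cohort and no hypothesis test attached. Two unaffected per-mg measures stand in the same SAP sentence, concentration-time plots are planned, and Protocol 16.7 lists clearance where it can be estimated. AUCt over the actual first interval is also a valid description of exposure over that interval. All of that stands, and it limits the consequence.

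A reader might infer more than the documents support:

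- *That the report would conclude PK is nonlinear.* Linearity and proportionality assessments are optional, and first-dose AUCt is not named as their metric. The unaffected rows would point the other way.
- *That the Phase 3 dose choice is at risk.* The dose rationale in Protocol 6.2 rests on population PK half-life, a target trough and pooled PK/PD data, not on this row.
- *That comparing doses is a stated secondary objective.* Protocol 5.2 speaks of the PK and PD effects of multiple doses. Dose proportionality is neither an objective nor an endpoint.
- *That every cohort comparison is off by 1.4- to 1.8-fold.* Those factors apply to Cohorts 2 and 4 against Cohorts 1 and 3, and they assume one compartment.

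The reply does not remove the defect itself. The summary is a commitment, its natural use is a comparison across doses, and neither document warns that the windows differ.

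**Conclusion.** The point holds as a limited one: first-dose exposure per mg, as planned, cannot be compared across all four cohorts. The window lengths follow directly from the schedule, given that the drug is still quantifiable at Dose 2.

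The sizes rest on linear PK and the documents' half-lives. Relative to Cohorts 1 and 3, dose-normalised AUCt is inflated about 1.4-fold in Cohort 2 and 1.7- to 1.8-fold in Cohort 4 under one compartment. The assumed distribution phases give about 1.3-1.4 and 1.5-1.8. Cohort 4 against Cohort 2 is about 1.26 under one compartment and smaller with a distribution phase. Cohort 1 against Cohort 3 is sound. No efficacy or safety conclusion depends on this.

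**What to change.** In SAP 7.2.4.1:

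- Add AUC0-14d and dose-normalised AUC0-14d after the first dose in all four cohorts. AUC0-x is already defined in Protocol Table 2.
- State that these, not AUCt, support any first-dose linearity or dose-proportionality statement.
- Keep AUCt, because Protocol 16.7 lists it. Label it with each cohort's window (14, 21, 14 and 28 days) and mark it as not comparable per mg across cohorts.
- For Cohort 2, specify log-linear interpolation to Day 15 between the 4-hour and Day 22 predose samples. Flag in the table that the value may be about 4-10% high if there is a distribution phase.

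Record the added parameter in SAP 4.1, which currently declares no change from the protocol's analyses other than the Cohort 4 Day 281 data.

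The cost is SAP wording and a partial-area setting in the noncompartmental software, with no new samples. The remaining weakness is the interpolated Cohort 2 value. AUC(0-infinity) would also remove the window effect, but at a 43-day half-life only 20% (14-day window) to 36% (28-day window) of it is observed before Dose 2, so most of it would be extrapolated.

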7.2.4.2. Immunogenicity Analyses

All immunogenicity analyses will be conducted on the Immunogenicity Set. The number and percentage of subjects developing ADA will be summarized by cohort and overall.

7.3. Safety Analyses

All safety analysis will be conducted on the Safety Set. All safety data available at the time of database lock up to Day 253 (Day 281 for Cohort 4) will be provided in patient listings. AEs will be encoded in the latest available version of standardized Medical Dictionary for Regulatory Activities (MedDRA) and presented by system organ class (SOC) and preferred term (PT). Patients having multiple AEs within a category (e.g., overall, SOC, PT) will be counted once in that category. For severity/relationship tables, the patient's highest grade/most related event within a category will be counted. No formal hypothesis testing will be performed.

7.3.1. Study Duration, Treatment Compliance, and Exposure

Summary statistics (mean, standard deviation, median, minimum, and maximum) will be produced for the following using the Safety Set:

- Number of infusions from Day 1 to Day 253 (Day 281 for Cohort 4)
- Total number of patients with an infusion interruption as well as total number of infusions interrupted from Day 1 to Day 253 (Day 281 for Cohort 4)
- Duration of study participation from informed consent to Day 253 (Day 281 for Cohort 4)
- Total time on study treatment (days) from Day 1 to Day 253 (Day 281 for Cohort 4)

The frequency and percentage of patients who had a percentage of drug compliance range by increments of 10% (i.e. $\geq 90\%$ to $\leq 100\%$; $\geq 80\%$ to $< 90\%$; etc) will also be included.

By-patient listings will be produced for study duration, treatment compliance and exposure.

7.3.2. Adverse Events (AEs)

Adverse Events (AEs) will be classified by System Organ Class (SOC) and Preferred Term (PT) using the latest available version of MedDRA and will be reported by cohort and overall. The adverse events will be determined as occurring prior to treatment (pre-treatment) or as on or after first treatment (treatment-emergent) as described in Section 9.4. Analyses of Pre-Treatment Adverse Events (PTAEs) and Treatment-Emergent Adverse Events (TEAEs) will be tabulated and presented separately. Patients having multiple AEs within a category (e.g., overall, SOC, PT) will be counted once in that category. For severity/relationship tables, the patient's highest grade/most related event within a category will be counted. Percentages will be based on the number of treated patients in the Safety Set within a cohort and overall. Tables will be sorted by descending frequency of SOC and by descending frequency of PT within SOC.

Listings will be provided for all TEAEs and PTAEs for the Safety Set.

AEs will include the displays described in the following sub-sections

7.3.2.1. Overall Summary of Adverse Events

All TEAEs will be presented using summary statistics (n, %). The number of events (n) and number of patients with events (n, %) will be displayed for the following events subcategories:

Table 2: Treatment-Emergent Adverse Events (TEAEs) and Serious TEAEs

Relationship	Severity
Related AEs (Possibly, Probably, or Definitely Related)	Grade 1 AEs
Not Related AEs (Not Related or Unlikely Related)	Grade 2 AEs
	Grade 3 AEs
	Grade 4 AEs
	Grade 5 AEs

Additionally, the number and percentage of patients who withdraw from the study due to an AE or who die will be presented. These statistics will be prepared separately for all TEAEs and SAEs.

